- **Acceptability** will involve establishing the safety profile of 3 times weekly low dose ferrous sulphate (65mg elemental iron) supplements among deferred prospective blood donors with ID and IDA. This safety profile will be established by comparison to a similar group of participants who do not receive iron supplementation. Participant and key informant views and perspectives of barriers and recommendations for using iron supplementation and nutritional counseling to increase the blood donor pool will also be investigated with participant questionnaires. In addition, focus group discussions and key informant interviews will provide critical insights into the acceptability of this intervention.
- **Key blood donation measures** include haemoglobin levels at 4 months, the change in haemoglobin concentration, ferritin levels at 4 months, the proportion of participants with corrected ID, the proportion of participants who return to the blood centre to donate blood and the proportion of returners who are able to successfully donate (not deferred). In addition, the incidence of ID and IDA among blood donors will be determined using a group of participants who were not deferred, were not ID and did not have IDA at baseline.

To achieve this objective, a pilot study will be conducted for one year. This allows for enrolment over a maximum of 6 months and 6 months of follow-up for the last individual enrolled. The follow-up period incorporates 4 months of the iron supplementation intervention.

Secondary Objectives

- To determine changes in haemoglobin in blood donors over a 6-month period.
- To determine the impact of iron supplementation on the change in haemoglobin.
- To estimate the prevalence of iron deficiency and iron deficiency anaemia in prospective first-time blood donors.
- To determine the factors associated with iron deficiency and iron deficiency anaemia among prospective blood donors.
- To determine the prevalence of malaria or adverse events among the prospective first-time blood donors.
- To identify the barriers and facilitators of repeat donation and the use of dietary and iron supplementation interventions to address iron deficiency and/or anaemia among blood donors.
- To determine feasibility of the intervention, through documenting implementation fidelity, intervention adaptation, and intervention strengths and weaknesses.
- To understand participant and key informant acceptance of the intervention.

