Since not all participants will consent to participate in the study and only a subset of donors are first-time donors, the precision of estimates of the prevalence of ID and IDA will be lower. Based on the unpublished estimates of the prevalence of ID and IDA provided above (i.e., 63.9% of those with anaemia had IDA and 86.1% of those with anaemia had ID, so 30.7% of the total had IDA and 41.3% had ID), estimates of the prevalence of these conditions cover almost the same range as our estimates of the prevalence of low haemoglobin. Since enrolment for this component of the study entails enrolment in the longitudinal study, the sample size was determined by the requirements for the longitudinal study which is 292 participants. Since some participants in the cross-sectional study of ID and IDA may be found to have $Hb < 10\text{g/dl}$ and will therefore be excluded from the longitudinal study, the sample size for the cross-sectional study may exceed 292. This will require that, on average, almost 2.5 participants per day consent to the study to get to about 300 over the 6-month enrolment period. Table 2 shows values for the prevalence of ID/IDA, the corresponding margin of error and the corresponding 95% confidence interval. For example, if the prevalence of IDA is 30% then a 95% confidence interval would be (25%, 35%) which has a total width comparable to the confidence intervals obtained using all potential donors.

Table 2: Precision of prevalence estimates for ID and IDA.

| Prevalence | Margin of error | 95% confidence interval |
|------------|-----------------|-------------------------|
| | | |

| | | |
|-----|-------|------------|
| 0.2 | 0.046 | 0.15, 0.25 |
| 0.3 | 0.053 | 0.25, 0.35 |
| 0.4 | 0.056 | 0.34, 0.46 |
| 0.5 | 0.057 | 0.44, 0.56 |

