There are 3 components of the quantitative study (observational study of deferral, observational study of the prevalence of ID and IDA, and the clinical trial of supplementation) with slightly different inclusion and exclusion criteria, hence we indicate which criteria apply to which component of the study below.

Items 1-3 are required for the observational study of deferral, items 1-4 are required for the observational study of the prevalence of ID and IDA and items 1-5 are required for the clinical trial. Only participants who meet ALL the following inclusion criteria will be eligible for the clinical trial:

1. Males or females aged between 17 and 60 years who weigh at least 50kg.
2. Pass pre-donation screening using the NBSG standardised donor screening questionnaire for medical conditions and lifestyle risks for transfusion transmissible infections (Appendix 5).
3. Vital signs must meet the NBSG requirement for blood donation: systolic and diastolic blood pressures between 90-140 mmHg and 60-90 mmHg, respectively; pulse rate between 50-100 bpm; non-contact forehead temperature not exceeding 37.5°C; meeting acceptable requirements for skin lesions, needle marks and physical appearance.
4. Must be willing and able to give study consent or assent.

5. Intend to remain in the study location/site during the entire length of the study.

Exclusion Criteria

There are no additional exclusion criteria for the observational study of deferral, items 1-2 are required for the observational study of the prevalence of ID and IDA, and items 1-5 pertain to the clinical trial. All persons who meet ANY of the following exclusion criteria will be excluded from participating in the clinical trial.

1. Persons who have used iron supplementation within the past one month.
2. Participant reports having previously donated blood.
3. Evidence for a TTI at baseline among those who successfully donated.
4. Evidence of Malaria and helminthic infections at baseline
5. Participants who have Hb <10g/dl at screening

Potential donors who are found to have Hb < 10g/dl at screening will be referred for further evaluation and care by a haematologist. Any clinical trial participant found to have Hb < 10g/dl at any follow-up visit will be referred for evaluation by a haematologist.

Approach to Inter-current Therapies and Clinical Trial Co-enrolment:

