Individuals in blood donor groups will proceed with routine assessment by blood donation staff for eligibility for whole blood donation as defined by the NBSG. As part of this assessment, these potential blood donors will undergo routine semi-quantitative haemoglobin assessment using the copper sulphate (CuSO_4) gravimetric method with a cut- off Hb concentration value of <13.0 g/dL for males and <12.0 g/dL for females. Prospective blood donors who consent and meet the eligibility criteria will be eligible for the study. The site will log potential blood donors who are approached to participate in the study and document whether the participant elects or declines involvement with the study.

- *Consenting Procedure*

Prospective blood donors who pass all pre-donation assessments, and those who are deferred specifically on account of failed CuSO_4 will be approached and informed about the study by trained research assistants. All eligible participants will provide written informed consent and, in the case of minors, additional assent. Eligible enrolled minors who turn 18 during the course of the study will need to be re-consented as adults.

- *Rescreening*

Rescreening will be allowed for previously excluded participants after four months. In this case a new study identification number will be assigned to the participant and the participant will be identified with this new number for the rest of his/her participation in the study. If participant has been enrolled, re-screening is not allowed. In case rescreening occurs, all evaluations re-assessed should meet the eligibility criteria. A new informed consent form (ICF) must be signed only if there is an interruption in the participant's eligibility evaluation and the investigator chooses to re-screen the participant following screen failure. If a new ICF is signed,

AEs and medical history will be assessed relative to the new informed consent date.

- *Blood Sampling:*

Participants who consent/assent to participate will have 5ml of whole blood sampled into an EDTA tube for full blood count, peripheral film comment, malaria rapid test and plasma ferritin analysis. This blood draw will take place prior to donation for those participants who can donate to prevent a classification of ID due to sampling immediately after a donation.

- *Estimation of Iron Deficiency and Iron Deficiency Anaemia*

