The investigator will be responsible to ensure only participants who meet all inclusion and none of the exclusion criteria are included in this study. Following registration for screening, participant eligibility will be checked once all screening procedures are completed.

- ***Screening failures***

Participants who sign an ICF and are subsequently found to be ineligible prior to enrolment will be considered a screen failure. The reason for screen failure should be recorded on the appropriate eCRF. The demographic information, informed consent, and Inclusion/Exclusion pages must also be completed for screen failure participants. No other data will be entered into the clinical database for participants who are screen failures, unless the participant experienced a SAE during the screening phase (see SAE section for reporting details). Prospective donors who are found after baseline screening to have haemoglobin values less than 10g/dl will be referred to the haematology outpatient clinic or community clinic for further investigations and management. This includes participants who are found to have haemoglobin values less than 10g/dl at a follow-up visit. These participants will continue to be followed for the duration of follow-up. If use of iron supplementation is consistent with recommended medical care, the study will provide iron supplements to these participants and this will be captured in the study database.

Follow Up Assessments

The assessment schedule lists all of the assessments and indicates with an “X” (table 5), the visits when they are performed. All data obtained from these assessments will be entered into a database.

Study participants will be seen for all visits/assessments as outlined in the assessment schedule or as close to the designated day/time as possible. Participants who have not previously been provided with iron supplementation and

are found to have ferritin <15g/dl or low haemoglobin by the sex-based thresholds during study visits will be offered iron supplementation. This will be recorded in the study database and these participants will be followed for the duration of follow-up. Participants will be instructed to report missed doses to the study team and this will be documented. They will be instructed to wait till the next dosing day and not to double their dose. Missed or rescheduled visits will not lead to automatic discontinuation.

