### 3.4 Baseline characteristics

Baseline characteristics for those who enrol in the trial will come from information collected on the screening and enrolment forms. The only characteristics captured for those in the anaemia deferment study are age, sex, if the person has previously donated, and the type of donation (i.e., replacement/family or voluntary). For those in the study of ID/IDA information on abnormal peripheral blood film, malaria, haemoglobin, ferritin, and TTI status will also be obtained. Additional information will be available for those in the trial. For the open report, baseline characteristics will be summarized pooled across the two treatment groups and presented separately for those in the anaemia deferment study, the ID/IDA study, and the trial. Note that these study populations are related as follows: everyone in the trial is in the ID/IDA study, and everyone in the ID/IDA study is in the anaemia deferment study. Note that someone who consents to the trial but is found to have levels of haemoglobin that are too low at screening will participate in the ID/IDA study but will not participate in the trial.

For the closed report, baseline characteristics will be summarized by treatment group for the Iron Supplementation Trial.

The following baseline characteristics will be summarized with counts and percentages for binary and categorical variables, medians and quartiles for continuous variables and ordinal variables when available for each of the 3 components of the study.

Demographics:

- Age: summary as continuous variable.
- Sex.
- First-time donation status (Yes or No).
- Number of children (an integer equal or above 0).
- Marital status (6 options).
- Home situation (6 options).
- Main method of travel (private or public).
- Highest level of education completed (7 options).
- Employment category (8 options).
- Number of expensive, durable consumer items (an integer in the range 0-7).
- Ethnic background (6 options).
- Religion (5 options).

Screening laboratory results:

- Haemoglobin concentration.
- Plasma ferritin concentration.

- Malaria test results from a malaria rapid diagnostic test.
- Abnormal peripheral blood film results reported by type of abnormality (i.e., helminthic infection, malaria, neutrophilia, leucocytosis, and lymphocytosis).
- ID present
- IDA present.

Medical History:

- Diagnoses (19 options, select all that apply).

Nutritional History:

- Number of meals yesterday (4 options).

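### The Protocol's screen-failure data rule conflicts with membership of the ID/IDA prevalence study and, applied literally, would leave donors with Hb below 10 g/dL unclassified

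*Protocol*

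**What the plan says.** **The data rule.** Protocol, Enrolment, Screening failures: "Participants who sign an ICF and are subsequently found to be ineligible prior to enrolment will be considered a screen failure". No study component is named, and the eligibility check just above it asks for every inclusion criterion and no exclusion criterion. The failure reason is recorded, and "The demographic information, informed consent, and Inclusion/Exclusion pages must also be completed for screen failure participants". Apart from an SAE during screening, "No other data will be entered into the clinical database for participants who are screen failures".

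**Who belongs to the prevalence study.** Protocol, Exclusion Criteria (repeated in SAP 3.1): "items 1-2 are required for the observational study of the prevalence of ID and IDA, and items 1-5 pertain to the clinical trial". Items 3 to 5 (TTI among those who donated, malaria and helminths, Hb below 10 g/dL) therefore exclude from the trial only. The Protocol's sample size justification says that, because donors below 10 g/dL count in the cross-sectional part, "the sample size for the cross-sectional study may exceed 292". SAP 3.4 says that a consenting donor whose haemoglobin is too low "will participate in the ID/IDA study but will not participate in the trial", and lists film, malaria, haemoglobin, ferritin and TTI status as obtained for the ID/IDA study. SAP 3.3 defines that study's analysis population as all who are eligible and consented.

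**The objectives served.** Prevalence of ID and IDA in first-time donors is a secondary objective and a named design component. Another secondary objective is "To determine the prevalence of malaria or adverse events among the prospective first-time blood donors".

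**The concern.** ID and IDA are defined by haemoglobin and ferritin together (Protocol Table 4). A site or database builder who follows the screen-failure paragraph would enter neither value for a donor excluded from the trial on laboratory grounds. That donor belongs to the prevalence study but cannot be classified.

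The loss is selective. It removes the lowest haemoglobin values, where anaemia is certain, so the study drifts towards describing trial-eligible donors only. The row of Table 4 for Hb below 8.0 g/dL would be empty in the database. The planned comparison of copper sulphate with the analyser would also have no values below 10 g/dL. Nothing in the SAP says that it overrides the Protocol's data-entry rule.

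**Working it through.** **Reproducing the plan's figures.** Anaemia 48%, of which 63.9% IDA and 86.1% ID (Protocol, Problem Statement): 0.48 × 0.639 = 0.307 and 0.48 × 0.861 = 0.413, matching the stated 30.7% and 41.3%. Margin at 30% prevalence with n = 292: 1.96 × √(0.3 × 0.7/292) = 0.0526, matching 0.053 in Table 2.

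**Share of donors below 10 g/dL (f)**, normal with SD 1.89:
- Stated mean 13.4: Φ((10 − 13.4)/1.89) = 0.036.
- Half-anaemic illustration used for the margin (means 13.0 for men, 11.5 for women): Φ(−3.0/1.89) = 0.056 for men and Φ(−1.5/1.89) = 0.214 for women.
- Pooled, with an assumed 60% men: 0.6 × 0.0562 + 0.4 × 0.2137 = 0.119. With 80% men: 0.8 × 0.0562 + 0.2 × 0.2137 = 0.088.

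**Assumption.** Let q be the share of donors below 10 g/dL who have IDA. The documents do not give it. I take q = 0.639, the share among all anaemic donors, and show q = 1 as the upper limit.

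**Shift in the unweighted proportion.** With starting prevalence P, the prevalence left is (P − f·q)/(1 − f).

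| Scenario | P | f | q = 0.639 | q = 1 |
|---|---|---|---|---|
| Mean 13.4 | 30.7% | 0.036 | 29.5% (−1.2) | 28.1% (−2.6) |
| Half anaemic, 80% men | 0.5 × 0.639 = 32.0% | 0.088 | 28.9% (−3.1) | 25.4% (−6.5) |
| Half anaemic, 60% men | 32.0% | 0.119 | 27.6% (−4.3) | 22.7% (−9.2) |

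**After the SAP 7.1 post-stratification.** The copper sulphate cut-offs are 13.0 g/dL (men) and 12.0 g/dL (women), so donors below 10 g/dL lie essentially within the failed stratum. The stratum's weight comes from the deferral data and is intact. Its remaining members stand in for the lost ones. If r is the IDA share among the remaining failed donors, the residual bias is −f(q − r).

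In the half-anaemic illustration, all IDA lies in the failed stratum. Its size w is 0.5 for men and Φ(0.5/1.89) = 0.604 for women, so w = 0.521 with 80% men and 0.542 with 60% men. Then r = (0.3195 − f·q)/(w − f).
- q = 0.639: r = 0.608 and 0.576; bias −0.088 × 0.031 = −0.3 points and −0.119 × 0.063 = −0.8 points.
- q = 1: r = 0.535 and 0.474; bias −0.088 × 0.465 = −4.1 points and −0.119 × 0.526 = −6.3 points.

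Post-stratification therefore corrects the weight of the failed stratum but not its composition. What remains depends on how much more common IDA is below 10 g/dL than in the rest of that stratum.

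**The case against.** The best defence is that eligibility is set per component. A donor below 10 g/dL is eligible for the ID/IDA study, so need not count as a screen failure at all. SAP 3.4 says outright that such donors take part, and the open report described in SAP 3.1 tabulates Hb, malaria, helminths and TTI as reasons for non-enrolment. This shows the intent, but it does not cancel the rule, which names no component and follows a check against all criteria. The Protocol also says that all data from the scheduled assessments go into a database, and Table 5 lists the screening tests. That sentence stands under Follow Up Assessments, so it does not settle the matter.

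The size should not be exaggerated either. The half-anaemic case is an illustration for the margin. The Protocol expects fewer than half to be anaemic, describes donors as unlikely to be severely anaemic, and says the SD may be slightly inflated. That stands.

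Four stronger readings are tempting, and the documents do not support them:
- **That these donors are planned to drop out.** The loss follows only from literal use of one paragraph against several others.
- **That all malaria-positive donors vanish.** The failure reason and exclusion page are still entered, so they remain largely countable, although Protocol item 4 merges malaria with helminths.
- **That rescreened people, to whom "a new study identification number will be assigned to the participant", are already counted twice.** Under the literal rule their first results are never entered, so they cannot be classified twice.
- **That the bias in women exceeds the stated margin.** The 5.3 points apply to all 292 participants, and no sex-specific prevalence estimate is planned.

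Nor is every loss in the failed copper sulphate stratum. TTI exclusions concern people who donated, and malaria can occur in either stratum.

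**Conclusion.** The conflict is real and should be fixed. Followed literally, the screen-failure rule withholds the haemoglobin and ferritin values needed to classify donors whom both documents place in the ID/IDA study.

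At q = 0.639 the unweighted IDA estimate falls by about 1.2 points under the stated mean and SD, and by 3.1 to 4.3 points in the half-anaemic illustration with an assumed 60-80% men. These are within the 5.3-point margin, but they are systematic, and a confidence interval does not cover them. The planned post-stratification reduces the illustration's shift to under 1 point if IDA is equally common at every anaemic Hb level. It leaves 4.1 to 6.3 points if every donor below 10 g/dL has IDA. The downward direction of the post-stratified bias rests on IDA being more common below 10 g/dL than among the other failed donors. Losses from malaria, helminths and TTI would come on top; the documents give no rates for them.

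The primary endpoint, its analysis and the sample size are unaffected.

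**What to change.** 1. In the Protocol's Screening failures paragraph, define screen failure separately for each study component.
2. For every consented donor who meets inclusion items 1-4 and neither of exclusion items 1-2, enter the copper sulphate result, FBC, ferritin, film comment, malaria RDT and any available TTI status, whether or not the donor joins the trial.
3. State that denominator in SAP 3.3 and 7.1.
4. Once these data are entered, link old and new identification numbers and use only the first screening of anyone rescreened.

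The cost is a few sentences and the entry of results already produced. No new procedure or blood draw is needed.

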Anaemia is a state in which the amount of red blood cells (RBCs) is insufficient to meet the body's physiologic needs ²⁴. Mild anaemia is defined as Hb ranging from 11-12.9 g/dL in adult males and 11-11.9 g/dL in adult females. Moderate anaemia is defined as Hb level of 8-10.9 g/dL and severe anaemia is defined as Hb level of less than 8 g/dL for all the age groups ^{25,26}.

Following FBC and plasma ferritin estimation, screened participants will be classified by the WHO criteria as shown in Table 4:

Table 4: Definition of Iron Status Criteria

| Haemoglobin concentration, g/dL | Plasma ferritin concentration µg/L | Interpretation |
|--|------------------------------------|---|
| [Male] >13.0 [Female] >11.5 | < 15 | Iron deficiency without anaemia |
| [Male] ≥8.0-13.0 [Female] ≥8.0-11.5 | < 15 | Iron deficiency with mild to moderate anaemia |

| | | | |
|-------|------|------|-------------------------------------|
| [All] | <8.0 | < 15 | Iron deficiency with severe anaemia |
|-------|------|------|-------------------------------------|

Schedule of Assessments (Table 5)

| Assessment | Screening (Day -14 to 0) | Enrolment (Day 0) | Biweekly (Throughout) | Interim Visit 1 | Interim Visit (Week 8-10) | Interim Visit 2 | Final Visit (Week 24) |
|--|-----------------------------|----------------------|--------------------------|--------------------|------------------------------|--------------------|--------------------------|
| NBSG Pre-Donation Assessment | X | | | | | | X |
| Informed Consent | X | | | | | | |
| Inclusion and Exclusion Criteria | X | | | | | | |
| Demographics | X | | | | | | |
| Full Blood Count and peripheral blood comment | X | | | X | X | X | |
| Plasma Ferritin | X | | | X | X | X | |
| Malaria Parasites Testing (RDT) | X | X | | X | X | X | |
| Nutritional Counselling | | X | | X | X | X | |
| Qualitative Assessment | | | | | | | X |
| Follow-Up Calls | | | X | | | | |
| Return Blood Donation Status | | | | X | X | X | X |
| Assessment for Adverse Events | | X | X | X | X | X | X |
| Adherence Assessment (for those receiving supplemental iron) | | | X | X | X | X | X |
| RDT – Rapid Diagnostic Test | | | | | | | |

Enrolment

Participants will be re-assessed with their laboratory results at the Day 0 visit.

- ***Eligibility Check***

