Participants will be followed up every 2 months and will be interviewed by members of the research team and appropriate CRFs completed by study staff. Adherence to iron supplementation and nutritional counseling will be assessed biweekly by phone and at each visit.

Participants with suspected adverse events of iron supplementation will be appropriately managed. Participants with suspected bacterial infections will be assessed with blood cultures (if indicated) and tested for malaria parasites during study visits. Malaria preventive measures will be discussed with all study participants on enrolment, and they will be encouraged to use these preventive measures throughout the study. A history of medical events and selected potential adverse events will be obtained at each scheduled visit and during biweekly follow up phone calls. Participants will also be given identification cards to carry with them at all times providing instructions directed to any health care provider who sees them for an unscheduled medical care visit.

- ***Treatment***

The planned duration of treatment is 4 months. Participants with a low plasma ferritin <15 μ g/L, with or without anaemia, will be given oral iron supplementation and nutritional counseling. Treatment will continue for 16 weeks or until the end of follow-up, during which participants will be followed up for adherence counseling at each visit. Clear written instructions for use 3 times a week will be discussed with them. Research staff will contact participants every 2 weeks by phone for adherence and feedback, and to remind participants to keep their scheduled study visits.

Testing of plasma ferritin and FBC after 4 months of supplementation will allow us to assess for response to study treatment with regards to iron stores. After correction of iron depletion or IDA, FBC and plasma ferritin will be monitored at 4 months from baseline. Participants after the end of the intervention phase still found to be iron deficient or anaemic will continue management and further evaluation at the haematology clinic.

- **Discontinuation**

If discontinuation of study treatment occurs, the investigator should make a reasonable effort to understand the primary reason for the participant's premature discontinuation of study treatment and record this information.

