## 4 Administration of Study Treatment

Potential first-time donors will be asked if they are interested in participating in a study of the prevalence of ID and IDA and the impact of iron supplementation on haemoglobin levels and repeat donation. Those who express interest, consent to the study, and are eligible will be asked to return within 3 weeks. During this 3-week period a FBC, a peripheral blood film analysis, and a plasma ferritin measurement will be conducted, and participants will be classified as iron supplement participants (e.g., anaemic, ID, IDA) or otherwise (which we refer to as controls in this protocol).

Those found to be anaemic, ID or IDA will receive oral iron supplementation and nutritional counselling. The oral iron supplements will be ferrous sulphate 200mg (65mg Elemental iron). The iron supplements are already available at the Korle-Bu Teaching Hospital Pharmacy. The study principal investigators and study pharmacist will ensure the medicine is stored properly and dispensed only when needed for study participants. The following will be monitored and completed on a periodic basis to ensure the medicine is within study guidelines, pharmaceutical compliance, and manufacturer guidelines:

Drug Accountability Record.

Iron supplement Safety and Handling Sheet.

Controls will not be given iron supplementation at enrolment but will receive the standard practice of nutritional counselling for blood donors. If someone not given iron supplements at enrolment is found to be anaemic, ID or IDA at a follow-up visit that individual will receive iron supplements.

All study participants will have nutritional counselling, dietary advice, and for those

receiving iron, the need for iron therapy to be used consistently 3 days a week.

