#### Primary analysis

The analysis for the primary outcome of haemoglobin levels at 4 months will be conducted using a linear model with haemoglobin levels at 4 months as the response variable. It is unlikely that there is a need to transform the response variable as haemoglobin levels are usually symmetrically distributed with tails that decay at rates consistent with the normal distribution. However, if informal univariate assessments of normality (e.g., qq-plots) indicate strong departures from these expectations, the Box-Cox transformation will be used to select a transformation. The set of explanatory variables will be group membership (i.e., received iron supplementation at enrolment or not), screening haemoglobin, sex, and age. A 1-sided t-test for the regression coefficient associated with group membership will be conducted with a significance level of 0.025 to test the inferiority hypothesis. This analysis will exclude individuals who did not receive iron supplementation at enrolment but received it during follow-up due to changes in ferritin or haemoglobin values. The frequency of this will be closely tracked and if more than 10% of participants in the group initially not receiving iron supplementation receive iron supplementation during follow-up, alternative analysis approaches will be considered and presented to the DSMB.

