## 7.2.2 Secondary outcomes

### Secondary outcomes related to efficacy

Several secondary outcomes relate to the efficacy of iron supplementation. The treatment of those not requiring iron supplementation at enrolment but requiring iron supplementation during follow-up will be the same as for the primary outcome. These secondary outcomes include:

- Change in haemoglobin over 4 months (g/dl).
- Ferritin levels at 4 months (µg/L).
- Diagnosis of ID or IDA at 4 months (Yes or No).
- Attempt to return for donation within 6 months (Yes or No).
- Successful donation within 6 months (Yes or No).

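### The protocol's follow-up rule for offering iron prints the ferritin threshold in g/dl, which conflicts with the µg/L of Table 4 and the Treatment paragraph

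*Protocol*

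**What the plan says.** Four places bear on when a participant is given iron.

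- **Protocol, Follow Up Assessments.** The rule covers people not yet given iron. They are to be offered it if, at a study visit, they "are found to have ferritin <15g/dl or low haemoglobin by the sex-based thresholds".
- **Protocol, Table 4 (iron status criteria).** The ferritin column is headed "Plasma ferritin concentration µg/L", and every row uses a cut-off below 15.
- **Protocol, Treatment paragraph**, which also falls under Follow Up Assessments. Participants with plasma ferritin below 15 µg/L, "with or without anaemia, will be given oral iron supplementation and nutritional counseling".
- **SAP section 4.** The trigger is stated by diagnosis, with no ferritin figure: "If someone not given iron supplements at enrolment is found to be anaemic, ID or IDA at a follow-up visit that individual will receive iron".

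The SAP gives a ferritin unit in section 7.2.2, where the outcome is listed as "Ferritin levels at 4 months (µg/L"). It does not state a ferritin cut-off anywhere.

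The rule feeds the analysis through SAP 7.2.1: "This analysis will exclude individuals who did not receive iron supplementation at enrolment but received it during follow-up". The protocol's Quantitative Data Analysis section has the same exclusion, and both documents handle the secondary efficacy outcomes the same way. If more than 10% of the group initially without iron starts it, alternative approaches are to be considered and taken to the DSMB.

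**The concern.** The follow-up sentence attaches to ferritin the unit that the documents use for haemoglobin. It is also the only sentence in either document that gives a ferritin number specifically for participants who were not on iron at enrolment. Table 4 is introduced for classifying screened participants, and the Treatment paragraph describes the planned four-month course.

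Two things depend on this threshold. One is exposure, since it decides which controls are offered study product. The other is the analysis set, since it governs who may leave the primary comparison and who counts toward the 10% limit. A site that applies µg/L departs from the printed rule, and a monitor checking conduct against the protocol finds two statements that cannot both hold.

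**Working it through.** **1. The plan's own sample size, to see whether any figure depends on the unit.** Inputs from the protocol's Sample size justification and SAP 2.4: margin 1.0 g/dL, SD 1.89 g/dL, true difference -0.3 g/dL, one-sided alpha 0.025, power 85%.

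n per arm = 2 × (1.960 + 1.036)² × 1.89² / (1.0 - 0.3)² = 2 × 8.98 × 3.572 / 0.49 ≈ 130.9, so 131.

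Total = 2 × 131 = 262. With the 10% allowance, 262 / 0.90 = 291.1, so 292, or 146 per arm. Both figures match the plan, and the other rows of Table 3 (65, 80, 101, 179) also reproduce. Ferritin does not enter the formula.

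**2. The unit conversion.**

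15 g/dL × 10 dL/L = 150 g/L

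150 g/L × 1,000,000 µg/g = 150,000,000 µg/L

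150,000,000 / 15 = 10,000,000

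The printed threshold is therefore 10⁷ times that of Table 4, and any measurable ferritin falls below it.

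**3. What the literal reading would and would not do.**

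- All 146 planned controls would meet the rule at their first follow-up visit with a ferritin result.
- The rule covers only people not previously provided with iron, so a control who accepts it no longer falls under the rule at later visits.
- The rule says iron is offered, while the exclusion applies to those who received it. An empty control group in the primary analysis therefore also needs every control to accept.

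**4. How the primary analysis responds to the share of controls excluded.** This holds whatever the reason for starting iron. Normal approximation, 146 in the iron group with no loss, true difference -0.3 g/dL, and n_C controls remaining:

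power = Φ( 0.7 / (1.89 × √(1/146 + 1/n_C)) - 1.96 )

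| Controls excluded | n_C | Power |
|---|---|---|
| 0% | 146 | 88.6% |
| 10% | 131.4 | 86.9% |
| 20% | 116.8 | 84.7% |
| 30% | 102.2 | 81.9% |
| 50% | 73 | 73.4% |

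If the iron group also loses 10%, the 10% row becomes 85.1%, so the plan's allowance covers that case. The table shows why the rule that generates exclusions should be unambiguous. It does not forecast what the misprint will cause.

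**The case against.** The strongest reply is that nobody would apply the printed figure. If everyone qualified, the alternative condition of low haemoglobin would do no work. The rest of the protocol assumes that only some controls start iron: it allows 10% for loss or started iron, tracks whether more than 10% start, and plans to estimate incident ID and IDA in the control group. The µg/L threshold appears shortly afterwards under the same heading. The SAP does not repeat the misprint. Its diagnostic trigger, read with Table 4, would not give iron to a control with normal ferritin and haemoglobin.

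Most of this stands. A reader might infer from the printed threshold that every control would be put on iron at every visit and that the primary analysis would lose its control group. The documents do not support that. The unit can be inferred from the neighbouring text, the rule stops applying once iron has been provided, and exclusion requires that the iron be received. There are also safeguards. Above 10%, alternative approaches go to the DSMB. SAP 7.2.3 plans a sensitivity analysis that keeps these participants in the control group, and the protocol plans sensitivity analyses that place them in each group in turn.

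A reader might also infer that the SAP is in error for leaving the number out. That goes too far, because stating the trigger by diagnosis is legitimate when the protocol defines the diagnosis.

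The objection does not remove the contradiction. A rule for giving study product should not depend on the reader noticing that its unit disagrees with the table and paragraph around it.

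**Conclusion.** The inconsistency is real and confined to one sentence. The follow-up threshold as printed differs by a factor of 10⁷ from the one in Table 4 and the Treatment paragraph. If sites work in µg/L throughout, it has no numerical effect: 131 per arm and 292 in total stand, and the trigger is ordinary incident iron deficiency or low haemoglobin. Loss of the control group is only the extreme of a literal reading combined with full acceptance of iron. The analysis method in SAP 7.2.1 is not at fault on this point.

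The correction should still be made, because the sentence governs exposure to study product and helps define the primary analysis set. This conclusion assumes that the g/dl text is the protocol's own wording, and nothing in the documents suggests otherwise.

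**What to change.** Reconcile the ferritin unit in the Follow Up Assessments sentence with Table 4 and the Treatment paragraph, so that one threshold and one unit govern iron both at enrolment and during follow-up. The choice of threshold and unit is for the sponsor and its clinical team to confirm.

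Optionally, let SAP section 4 cite the reconciled definition beside its diagnostic trigger, since the exclusion and the 10% limit in 7.2.1 rest on it.

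The cost is a correction to one protocol sentence and, if wanted, one cross-reference in the SAP. The sample size, visits and analysis model do not change.
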